8.3. Setting

8.3.1. Inclusion criteria

Patients must meet all of the following inclusion criteria to be eligible for inclusion in the study:

1. Incident VTE diagnosis in an inpatient or outpatient setting (International Classification of Diseases 10th Revision [ICD-10]: I26.0, I26.9, I80.2, I80.3) between 1 Mar 2013 and 30 Jun 2019
2. Received anticoagulation therapy (all medication codes for anticoagulants approved for VTE in Korea; unfractionated heparin [UFH], low molecular weight heparin [LMWH], warfarin, and NOACs) within 30 days of their VTE diagnosis (the index date will be defined as the date of treatment initiation with anticoagulants)
3. Aged ≥ 18 years at index date

8.3.2. Exclusion criteria

Patients meeting any of the following criteria will not be included in the study:

1. Had a record of VTE diagnosis (ICD-10: I26.0, I26.9, I80.2, I80.3) within the 12-month period prior to the index VTE encounter.
2. Diagnosed with atrial fibrillation/flutter (ICD-10: I48), mechanical heart valve replacement (National Procedure Code: Z952, M6531, M6532, M6533, O1781, O1782, O1783, O1791, O1792, O1793, O1797, O1794, O1795, O1796, O1798, O1799) or mitral stenosis (ICD-10: I05.0, I05.2) anytime prior to index date.
3. Had a record of Inferior Vena Cava filter (National Procedure Code: O2045, M6650) anytime prior to index date.
4. Received anticoagulatory therapy within the 12-month period prior to index VTE encounter to restrict to new users of anticoagulatory therapy.
5. Prescribed two different anticoagulants on the same index date to prevent exposure misclassification.
6. Had a record of pregnancy (ICD-10: O03-O07, O10-O14, O16, O20-O026, O28-O36, O41-O43, O46.8, O46.9, O61-O66, O67.8, O67.9, O69, O70-O75, O80-O92, O94-O99, P08, Z33-Z39) within the 9-month period prior to index date.

7. Had a record of active cancer, defined as first diagnosis of cancer (ICD-10: C00-C97 [excluding non-melanoma skin cancer: C44]) with V code (V011, V027, V193, V194; a special code applied to patients with confirmed diagnosis of cancer by Korean Ministry of Health and Welfare for reimbursement for 5 years or longer if recurrent/metastasis) within the past 6 months of period prior to index date; or receiving anti-cancer treatment (chemotherapy, radiation therapy, or cancer related-surgery) under cancer diagnosis with V code within the past 6 months from index date (for Phase II of the study only). WHO-ATC codes and National Procedure Codes for anti-cancer treatment are shown in below table.

Anti-cancer treatment	WHO-ATC codes / National Procedure Codes
Chemotherapy	L01-04, H02AB02, H02AB04, H02AB06, H02AB07, H02AB09
Radiation therapy	HD051-HD059, HD061, HD071-HD073, HD080-HD089, HD091-HD093, HD110-HD115, HD121, HD150, HD160, HD211, HD212, HZ271
Cancer-related surgery	N0232, N0284-N0286, NA281-NA284, N0335, N0404, N0405, N0435-N0437, N0940, O0961-O0963, O1045, O1047, O1048, O1224-O1227, O1251, O1252, O1401, O1403-O1405, O1410, O1421-O1424, O1431, O1432, O1471, O1484, O1486, O1572, O1592, O1596, O1982, P2091, P2093, P2123, P2124, Q2150, Q2181-Q2183, Q2203, Q2206, Q2232, Q2292-Q2294, Q2346, Q2347, Q2348, Q2361, Q2362, Q2363, Q2365-Q2369, Q2401, Q2402, Q2403, Q2502, QA536, Q2533, Q2534, Q2536, Q2537, Q0251-Q0259, Q2594, Q2598, Q2601, Q2650, Q2651, QA671-QA673, QA679, Q1261, Q1262, Q2671-Q2673, Q2679, Q2761, Q2762, Q2791-Q2794, Q2796-Q2798, Q2890-Q2893, Q2901, Q0292, Q2921-Q2924, Q2927, Q2928, QA921-QA924, QA928, Q2925, Q2926, QA925, QA926, R3271, R3273, R3274, R3275, R3290, R3305, R3307, R3299, R3300, R3309, R3310, R3432, R3433, R3451, R3470, R3481, R3482, R3541-R3543, R3530, R3590, R3755, R3756, R3791, R3792, R3801, R3802, R3851, R3853, R3861, R3862, R3891, R3901, R3902, R3950, RZ512, R3960, R3975, R4003, R4004, R4067, R4068, R4071-R4074, R4140, R4143, R4144, R4147-R4149, R0141, R0142, R4154, R4155, R4156, R4250, R4331, R4332, R4423-R4428, P4543, P4551-P4554, P4561, P4571, P4572, S4616, S4634-S4639, S6691-6696, S4694-S4696, S4707-S4709, S4743, S4756-S4758, S4780, S4801-S4803, S4880, S4900, S4950, S5200, S5220, S5231, S5232, S5246, S5592, S5745, M6774, M6870, M6880, M6775, QZ841, M6890, M6900, M6991, M6910, Q0841, Q0842, N7136-N7139, N7140-N7153, Q7221-Q7225, Q7230, Q7280-Q7285, Q7342,

PFIZER CONFIDENTIAL

	Q7380, Q7410, Q7561-Q7567, Q7571, Q7572, Q7651-Q7654, Q7701-Q7703, QX706, Q7751, Q7752, Q7761-Q7763, Q7766, Q7771, Q7772, Q7775, Q7788, Q7789, U4811, U4812, U4881-U4883
Others	X5131-X5137 (hemopoietic cell transplantation)

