8.2. Study population

The study cohort will be defined as patients diagnosed with VTE between 1 Mar 2013 and 30 Jun 2019. The cohort entry will be defined as the date of incident VTE diagnosis. The index date will be defined as the date of first prescription for anticoagulants within 30 days after the index VTE event. The length of the exclusion assessment window will vary depending on the condition, from 12-months at minimum to anytime prior to index date. The following patients will be excluded: A record of VTE diagnosis within the 12-month period prior to the index VTE encounter, diagnosed with atrial fibrillation, atrial flutter, mechanical heart valve replacement or mitral stenosis anytime prior to index date, had a record of Inferior Vena Cava filter anytime prior to index date, received anticoagulatory therapy within the 12-month period prior to index VTE encounter to restrict to new users of anticoagulatory therapy, prescribed two different anticoagulants on the same index date to prevent exposure misclassification, had a record of pregnancy within the 9-month period prior to index date, and for the Phase II of the study only, had a record of active cancer within six months period prior to index date.

Baseline sociodemographic characteristics (e.g., age, sex) will be assessed on the index date, whereas clinical characteristics (comorbidities, previous use of medications, Charlson comorbidity index [CCI], HAS-BLED scores, initial presentation of VTE, number of outpatient visits) will be assessed in the 6-month period prior to the index date except when otherwise specified in section 8.4 *Variables* (Figure 2).

Within this study cohort, we will describe the treatment patterns of anticoagulants prescribed for VTE treatment throughout the period of follow-up, defined as the period from the index date to the end of the study period. Moreover, if feasible, we will also examine the risk of major bleeding overall and by site, associated with each NOAC use, as compared with warfarin.

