*Blood transfusion (Korean Procedure Codes: X1001, X1002, X2011, X2012, X2021, X2022, X2031, X2032, X2041, X2042, X2051, X2052, X2061, X2062, X2071, X2072, X2081, X2082, X2091, X2092, X2101, X2102, X2111, X2112, X2121, X2122, X2131, X2132, X2141, X2142, X3010) will also be used to define other site bleeding history.

- Initial presentation of VTE
 - DVT (I80.2, I80.3)

- PE (I26.0, I26.9)
- Both DVT and PE
- Comorbidities (ICD-10 diagnostic code) will be measured within the 6-month period prior to the index date.
 - Antiphospholipid syndrome (D68.6, I82.9): As diagnosis of antiphospholipid syndrome is usually made after VTE diagnosis with subsequent diagnostic procedures, its presence will be evaluated within the 6-month period after the index date.
 - Asthma (J45)
 - Cancer (C00-C97): History of cancer (non-active) will be evaluated within a lifetime prior to the index date.
 - Chronic obstructive pulmonary disease (COPD; J40-J44)
 - Chronic kidney disease (N18, N19)
 - Chronic liver disease (B18, B19, K70-K77)
 - Diabetes mellitus (E10-E14)
 - Fracture (S22, S32, S42, S52, S62, S72, S82, S92, T10, T12)
 - Heart failure (I50)
 - Hyperlipidemia (E78)
 - Hypertension (I10-I15)
 - Ischemic heart disease (I24, I25)
 - Myocardial infarction (I21)
 - Stroke (I60-I64, I69, G45)
 - Trauma (T79, T98, V01–V99, W11–W17, W50–W52, W64, X34–X39, Y01–Y04, Y30–Y32)
- Previous use of medications (WHO-ATC code) will be measured within the 6-month period prior to the index date.
 - Corticosteroids (H02)
 - Nonsteroidal anti-inflammatory drugs (NSAIDs; M01A)
 - Angiotensin-converting enzyme (ACE) inhibitors (C09A, C09B)

- Angiotensin II receptor blockers (ARBs; C09C, C09D)
- Antiplatelet agents (aspirin [N02BA01], aspirin/dipyridamole [B01AC30], abciximab [B01AC13], beraprost [B01AC19], cilostazol [B01AC23], clopidogrel [B01AC04], iloprost [B01AC11], indobufen [B01AC10], limaprost [C04AX], ozagrel [R03DX], prasugrel [B01AC22], sarpogrelate [B01AC], ticagrelor [B01AC24], ticlopidine [B01AC05], tirofiban [B01AC17], treprostinal [B01AC21], triflusal [B01AC18])
- Azole antifungal agents (fluconazole [J02AC01], itraconazole [J02AC02], voriconazole [J02AC03], posaconazole [J02AC04])
- β -blockers (C07)
- Calcium-channel blockers (C08)
- Selective serotonin reuptake inhibitors (SSRIs; N06AB)
- Proton pump inhibitors (PPIs; A02BC)
- Diuretics (C03)
- Thiazides (C03A)
- Vasodilators (C01D, C04A)
- Estrogens (G03C)
- Cyclooxygenase (COX)-2 inhibitors (M01AH)

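### The AF/valve exclusion and the diagnosis limb of the active-cancer exclusion stop before the index date, so a first code recorded on the day the anticoagulant starts does not exclude the patient

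*SAP*

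**What the plan says.** SAP 8.3.1 sets day 0: "the index date will be defined as the date of treatment initiation with anticoagulants". SAP 8.2 adds: "The index date will be defined as the date of first prescription for anticoagulants within 30 days after the index VTE event". Neither sentence rules out a start on the day of the VTE diagnosis.

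In SAP 8.3.2, exclusion 2 covers atrial fibrillation/flutter, mechanical valve replacement or "mitral stenosis (ICD-10: I05.0, I05.2) anytime prior to index date". Exclusion 7, active cancer, has two limbs. The diagnosis limb is a first cancer diagnosis with a V code "within the past 6 months of period prior to index date; or receiving anti-cancer treatment". The treatment limb is anti-cancer treatment "under cancer diagnosis with V code within the past 6 months from index date (for Phase II of the study only"). Protocol 9.2.2 repeats both criteria. The note to Figure 1 (SAP 8.1, Protocol 9.1) and the Protocol abstract instead place the treatment limb before the index date.

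On baseline variables, SAP 8.2 says: "initial presentation of VTE, number of outpatient visits) will be assessed in the 6-month period prior to the index date except when otherwise" specified in SAP 8.4. The SAP 8.4 entry headed "Initial presentation of VTE" gives DVT and PE codes and no window.

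**The concern.** Exclusions 2 and 7 exist to take out competing indications for anticoagulation and, in Phase II, cancer-associated VTE. The SAP introduction itself notes that NOACs are approved for nonvalvular atrial fibrillation as well as for VTE. A visit at which the drug is first prescribed is one at which such an indication could be recorded. If the look-back ends the day before, a patient given a NOAC or warfarin with a VTE code and a first AF code at the same visit remains in the cohort, although AF may be the reason for treatment. The same applies in Phase II to a cancer first registered that day.

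In Phase I, SAP 10 analyses cancer and non-cancer VTE separately, so the boundary decides which cohort a patient enters. A day-0 V code that misses the window could also be counted later, under SAP 8.4, as a new active-cancer event preceding a treatment change, if that change came within 30 days.

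**Working it through.** No figure in the plan depends on this boundary, so there is nothing to reproduce. The check sets the wording side by side and then applies the rule by day.

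**1. Does the plan distinguish day 0 from earlier days?** Yes.
- SAP 8.2 assesses age and sex *on* the index date and, in the same sentence, clinical characteristics *prior to* it.
- Exclusion 5, in the same list as exclusions 2 and 7, refers to two anticoagulants *on* the index date.
- Exclusion 2 and the diagnosis limb of exclusion 7 use *prior to* only.

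A programmer following the text would end those two windows at day −1.

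**2. Apply the rule by day.** Let day 0 be the index date and let the VTE diagnosis fall on day −L, with L from 0 to 30. Six months is taken as 183 days.

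| Item | Window ends day −1 | Window ends day 0 |
|---|---|---|
| First AF or valve code on day 0 | not excluded | excluded |
| First cancer V code on day 0 (diagnosis limb) | not excluded | excluded |
| Values of L with no VTE code in the 6-month window | L = 0 only | none |

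The last row follows because exclusion 1 removes anyone with a VTE code in the 12 months before the index VTE encounter. With L = 0, the only qualifying code lies on day 0. With L from 1 to 30, the code lies inside the 183 days.

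**3. Could the treatment limb catch the day-0 cancer patient?** Only if its phrase in SAP 8.3.2 is read to include day 0 and anti-cancer treatment is also recorded that day. Under the Figure 1 wording it could not. The two wordings need to be reconciled in any case.

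**4. Initial VTE presentation.** Read alone, SAP 8.2 leaves this variable without a value for same-day starters (L = 0). Two other places point elsewhere: Tables 1 to 4 have a row for the index VTE event, and the Phase I event list in SAP 8.4 refers to patients whose index event was DVT only. The Phase II balance shells, Tables 13 to 16, have no row for VTE type and so do not help. This is a conflict between sections.

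**5. Size.** The number affected is the number of patients with no earlier qualifying code whose first one falls on day 0. The documents give neither the share of same-day starters nor the share of conditions first coded on the start date, so no count and no shift in a hazard ratio can be calculated.

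**The case against.** The text never says that day 0 is left out. It is silent, and Figure 2, where window brackets would normally appear, is missing from the copy reviewed. That stands, and the conclusion is conditional on it.

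The affected group may be small. For exclusion 2, a patient needs an incident VTE code, no AF, flutter, valve or mitral stenosis code at any earlier time in the data, and a first one on exactly the start date. That also stands. A reader might infer that a large share of starters is affected, but nothing in the documents supports this.

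Ending look-back windows before treatment is a defensible convention, because codes on the start date cannot be ordered relative to treatment. This has force for comorbidity covariates. It also has force for exclusion 3: a day-0 vena cava filter may be part of managing the index VTE, and moving that boundary would remove those patients. It has little force for AF, valve disease or a confirmed cancer registration, which are not plausibly consequences of a drug started the same day.

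Three stronger readings are tempting and do not hold:
- **All windows end before the index date.** Exclusions 1 and 4 are anchored on the VTE encounter, the treatment limb of exclusion 7 runs from the index date in SAP 8.3.2, and antiphospholipid syndrome is assessed after the index date.
- **Same-day starters have no DVT/PE type.** Every included patient has an index VTE code, and other parts of the SAP take the type from that event.
- **The gap admits cancer patients to both phases.** Active cancer is an exclusion in Phase II only. Phase I keeps these patients by design, and the risk there is placement in the wrong cohort.

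**Conclusion.** The point holds for exclusion 2 and for the diagnosis limb of exclusion 7. Coded as written, both keep a patient whose first qualifying code is dated on the day the anticoagulant starts, against the purpose of the criteria. For cancer, the effect is inclusion in Phase II and, if the Phase I split uses the same definition, allocation to the non-cancer cohort.

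This rests on reading *prior to* as day −1 or earlier, which the plan's own usage supports, and on Figure 2 not stating otherwise. It is a minor point of unknown size, worth making because the correction is specific and nearly free. The wording on VTE presentation is a separate inconsistency between sections and does not show that the variable is lost.

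**What to change.** 1. In exclusion 2, and in both limbs of the active-cancer definition, write *on or before the index date*. Make SAP 8.3.2, Protocol 9.2.2, the Figure 1 notes and the Protocol abstract agree on the treatment limb.
2. Apply the same cancer window to the Phase I split into cancer and non-cancer cohorts.
3. Report how many patients the change removes from each phase and how many it moves between the Phase I cohorts.
4. Amend SAP 8.2 and Protocol 9.1 so that initial VTE presentation is taken from the index VTE event, in line with Tables 1 to 4 and the event list in SAP 8.4.
5. Leave day-0 handling of the vena cava filter and of the comorbidity windows to the sponsor, but state the choice.

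The cost is a phrase in each criterion, a few lines of code and slightly fewer patients. No new data are needed.

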NOACs, or also known as direct oral anticoagulants (DOACs), are a relatively new generation of anticoagulants approved by the US FDA; dabigatran, rivaroxaban, apixaban, and edoxaban were approved in October 2010, July 2011, December 2012, and January 2015, respectively, for treatment indication of risk reduction of stroke and embolism in nonvalvular atrial fibrillation (NVAF) [6]. These NOACs have also been approved for prophylaxis and treatment of DVT and PE, which comprise VTE [7, 8]. Compared with VKAs, NOACs have fewer drug interactions, food interactions, and adverse effects and therefore, do not require frequent laboratory monitoring or dosage adjustments [4, 9]. Among NOACs, apixaban and rivaroxaban were approved as a single-drug approach for the treatment of VTE and do not require initial parenteral treatment with low molecular weight heparin (LMWH) or unfractionated heparin (UFH) [10, 11]. In actual real-world clinical practice, the two aforementioned NOACs are the most widely used and preferred treatments for VTE and preventing its recurrence [12-14]. Although NOACs demonstrated better safety profile than VKAs, concerns regarding their risk of adverse bleeding events remain due to their mechanism of action [15].

With both conventional and new anticoagulant therapies being used in real-world clinical practice, it is necessary to identify the utilization characteristics of individual anticoagulant treatments through the analysis of nationwide claims database. It is important to examine the treatment pattern and assess whether Korean patients are being treated appropriately based on the current treatment guidelines.

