- The risk of major bleeding according to the treatment of interest will be investigated in time-to-event analyses using standard Kaplan-Meier methods.

- Cox proportional hazards model will be used to compare the safety outcome between users of different OACs, weighted on the estimated PS according to the IPTW approach.
 - Proportionality assumption will be tested by use of Schoenfeld residuals.

Subgroup Analysis

- The potential heterogeneity of treatment effects in selected subgroups of patients with VTE will be examined for the major bleeding as follows:
 - Aged <65 years vs. aged \geq 65 years
 - Females vs. males
 - Setting of VTE diagnosis (inpatient vs. outpatient)
 - Type of VTE (DVT without PE [ICD-10: I80.2, I80.3] vs. PE with or without DVT [I26.0, I26.9])
 - Major orthopedic surgery-provoked VTE
 - Major orthopedic surgery-provoked VTE is defined as an event preceded by knee arthroplasty, hip arthroplasty, or hip fracture surgery (National Procedure Codes: N0305, N0601, N0611, N0641, N0711, N2070, N0715, N2710, N0731, N0981, N0991, N1711, N3710, N1721, N3720, N1715, N4710, N1725, N4720, N2072, N2077, N2712, N2717, N3712, N3717, N3722, N3727, N4712, N4717, N4722 or N4727) within 3 months period prior to index date
 - With vs. without CKD stage 3 or 4 (N18.3, N18.4)
- P-for-interaction value <0.05 will be used to denote a significant difference between the two groups.

Sensitivity Analysis

- Vary the definition of treatment interruption/discontinuation to 15 and 60 days (allowing for varying non-adherence) to assess the effect this had on study outcomes.
- Four other approaches involving PS will be applied to determine the robustness of our study findings. First, we will vary the extreme value of PS in trimming process (most extreme 5%, and 10% will be excluded). Second, we will include the estimated PS, in addition to other covariates, into our multivariable Cox proportional hazards regression model. Third, we will stratify on the estimated PS in deciles. Last, we will apply another weighting approach, standardized mortality ratio weights, with the weights given as follows: 1 for the treatment group of interest and PS/(1 – PS) for the comparator group.[4]

- Exclude patients with a history of bleeding during the 6-month pre-index-date period in Phase II comparative analysis to evaluate the robustness of findings with respect to changes in underlying risk of patients

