Table 17. Risk of major bleeding events in patients with venous thromboembolism who newly initiated oral anticoagulants associated with NOAC use versus warfarin	58
Table 18. Risk of major bleeding events by site, intracranial, gastrointestinal, all others, associated with NOAC use versus warfarin.....	59
Table 19. Subgroup analyses for the risk of major bleeding events associated with NOAC use versus warfarin.....	60
Table 20. Sensitivity analyses for the risk of major bleeding events associated with NOAC use versus warfarin.....	62

Table 1. Baseline characteristics among venous thromboembolism patients without active cancer by their index anticoagulant treatment

Characteristics	Warfarin-based therapy N= (%)	NOAC-based therapy N= (%)	PAC only N= (%)	p-value
Follow-up (days; median, IQR)				
Age (years; mean±std)				
Age group (years; n, %)				
18-40				
40-65				
≥65				
Sex (n, %)				
Male				
Female				
Index VTE event (n, %)				
DVT only				
PE with or without DVT				
Major orthopedic surgery-provoked VTE (n, %)				
Health insurance type (n, %)				
National health insurance				
Medical aid				
Veterans				
Index year (n, %)				
2013				
2014				
2015				
2016				
2017				
2018				
2019				
CCI score (mean±std)				
HAS-BLED score (mean±std)				
Comorbidities (n, %)				
Antiphospholipid syndrome				
Asthma				
History of cancer				
COPD				
Chronic kidney disease				
Chronic liver disease				
Diabetes mellitus				
Fracture				
Heart failure				
Hyperlipidemia				

PFIZER CONFIDENTIAL

Hypertension

Ischemic heart disease

Myocardial infarction

Stroke

Trauma

Previous use of medications

(n, %)

Corticosteroids

NSAIDs

ACE inhibitors

Angiotensin II receptor

blockers

Antiplatelets

β-blockers

Calcium-channel blockers

SSRI

Proton pump inhibitors

Diuretics

Thiazides

Vasodilators

Estrogens

Cyclooxygenase-2

inhibitors

Triazole antifungal agents

Outpatient visits (mean±std)

Note: ACE, angiotensin-converting enzyme; CCI, Charlson comorbidity index; COPD, chronic obstructive pulmonary disease; IQR, interquartile range; NOAC, non-vitamin K antagonist oral anticoagulant; NSAIDs, nonsteroidal anti-inflammatory drugs; PAC, parenteral anticoagulants; SSRI, selective serotonin reuptake inhibitors; std, standard deviation.

Table 2. Baseline characteristics among venous thromboembolism patients with active cancer by their index anticoagulant treatment

Characteristics	Warfarin-based	NOAC-based	PAC only	p-value
	therapy	therapy		
	N=	N=	N=	

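### The orthopaedic surgery-provoked VTE row and subgroup are largely limited to patients with no recorded anticoagulant prophylaxis, which their labels do not say, and their surgery window runs back from first treatment instead of from the VTE

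*SAP*

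**What the plan says.** - **Washout.** Exclusion 4 in SAP 8.3.2 reads "Received anticoagulatory therapy within the 12-month period prior to index VTE encounter to restrict to new users of anticoagulatory therapy". Protocol 9.2.2 has the same rule. Neither makes an exception for indication, dose, duration or perioperative use, and neither attaches a code list to the criterion.
- **Study anticoagulants.** Inclusion criterion 2 in SAP 8.3.1 gives "all medication codes for anticoagulants approved for VTE in Korea; unfractionated heparin [UFH], low molecular weight heparin [LMWH], warfarin, and NOACs".
- **Prophylactic use is acknowledged.** Protocol section 7 notes that "These NOACs have also been approved for prophylaxis and treatment of DVT and PE".
- **Subgroup.** SAP section 10 states: "Major orthopedic surgery-provoked VTE is defined as an event preceded by knee arthroplasty, hip arthroplasty, or hip fracture surgery", with the operation falling "within 3 months period prior to index date". Protocol 9.7 uses the same definition.
- **Index date.** SAP 8.2: "The index date will be defined as the date of first prescription for anticoagulants within 30 days after the index VTE event". Cohort entry is a different date, that of the incident VTE diagnosis.
- **Where it is reported.** The category is a row in Table 1 (label beginning "Major orthopedic surgery-provoked VTE (n") and a stratum under VTE etiology in Table 19. Neither place mentions the washout.

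**The concern.** Two rules written for different purposes meet in this subgroup. The washout is there to secure new users. The subgroup is defined by operations after which some patients may be given an anticoagulant to prevent VTE. Where that happened and a VTE followed, the washout removes the patient, and the subgroup keeps mainly those with no such record.

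A reader of Table 1 would take the row as the frequency of surgery-provoked VTE among treated patients. A reader of Table 19 would take the hazard ratios as applying to surgery-provoked VTE without qualification. Protocol 9.9 encourages this by resting its statements on selection bias and generalisability on nationwide coverage, without discussing what the eligibility rules remove.

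The second problem is the anchor. Whether surgery provoked a clot depends on its timing relative to the clot, but the look-back is counted from first treatment.

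**Working it through.** The documents give no size, frequency or power for this subgroup, so there is no stated figure to reproduce. The check is on the definitions, followed by an illustration with assumed values.

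**Step 1: compare the windows.** Let day 0 be the VTE diagnosis and L the days from diagnosis to first anticoagulant, with L between 0 and 30 (SAP 8.2). Take 3 months as 90 days and 12 months as 365 days, and let the washout end at day 0. The surgery window then runs from L − 90 to L, and the washout from −365 to 0.

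| L | Surgery window | Days before diagnosis | Days after diagnosis | Share of window after diagnosis |
|---|---|---|---|---|
| 0 | −90 to 0 | 90 | 0 | 0% |
| 15 | −75 to 15 | 75 | 15 | 15/90 = 16.7% |
| 30 | −60 to 30 | 60 | 30 | 30/90 = 33.3% |

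The pre-diagnosis part is 60 to 90 days long and lies entirely inside the 365-day washout. A listed anticoagulant recorded after the operation and before the VTE encounter therefore always triggers exclusion 4.

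**Step 2: who still enters.**
- Patients with no drug prophylaxis.
- Patients given aspirin alone. SAP 8.4 lists it as a covariate under "Antiplatelet agents (aspirin [N02BA01], aspirin/dipyridamole [B01AC30", outside the study anticoagulants.
- Possibly patients whose VTE was diagnosed during the surgical admission. Inpatient VTE qualifies, and the washout ends at an encounter that is not defined at claim level, so prophylaxis within that admission may not count as prior.

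**Step 3: effect on the Table 1 share.** Let p be the share of surgery-provoked VTE before exclusion 4, q the fraction of those patients whom it removes, and r the fraction of all other patients whom it removes. Then

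observed share = p(1 − q) / [p(1 − q) + (1 − p)(1 − r)].

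None of the three values is in the documents; those below are assumptions. With r = 0 the formula becomes p(1 − q)/(1 − pq):

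| p | q = 25% | q = 50% | q = 75% |
|---|---|---|---|
| 10% | 0.075/0.975 = 7.7% | 0.05/0.95 = 5.3% | 0.025/0.925 = 2.7% |
| 5% | 0.0375/0.9875 = 3.8% | 0.025/0.975 = 2.6% | 0.0125/0.9625 = 1.3% |

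If r = q, the share stays at p. The frequency falls only if the washout removes surgical patients more often than the others. The study-size projection does not help to fix q or r, because its prior-treatment rule covered oral anticoagulants over 3 months only.

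**Step 4: the anchor.** Suppose an operation takes place after the VTE diagnosis and before the first anticoagulant. It lies inside the written window, and the later anticoagulant becomes the index treatment, so the washout does not remove the patient. At the other end, a patient first treated on day 30 loses any operation done 61 to 90 days before the VTE. Counting from diagnosis removes both effects.

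**The case against.** The strongest reply is that every subgroup is conditional on eligibility. The cohort is openly one of treated new users, exclusion 4 states its purpose, and within that cohort the Table 1 row has the right denominator. The stratum is one of six subgroup factors in a Phase II that is itself contingent on power, and the main comparison is untouched. All of this stands, and it limits the point to labelling and scope. It does not remove it: most exclusions have no special link to a particular subgroup, whereas this one acts directly on a treatment that may follow the defining operation.

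A reader might infer that every patient given drug prophylaxis is excluded and that only patients without prophylaxis remain. The documents do not support that. Aspirin does not trigger the washout, and prophylaxis within an admission that is itself the VTE encounter may not count as prior.

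On the anchor, one can answer that the definition already requires the event to be preceded by surgery, so an operation after the clot fails it. That is a fair reading of the intent. But the operational window says something else, and a programmer who applies the window alone would admit such cases. They are probably few. The inconsistency remains and takes a few words to remove.

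**Conclusion.** The point holds as one of scope and labelling, plus an inconsistent anchor. The row and stratum are largely limited to patients with no recorded UFH, LMWH, warfarin or NOAC before the VTE encounter, and neither document says so. This rests on reading exclusion 4 with the drug list of inclusion criterion 2, since the exclusion has no list of its own.

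The size cannot be computed from the documents. The shares in the illustration show what assumed values would do and are not estimates.

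Two further inferences are not supported. The first is that the Table 1 frequency is understated: within the new-user cohort it is correct by construction, and against a wider target the direction depends on losses among other patients, which are unknown. The second is that the subgroup hazard ratios are biased: the rule applies to all drug groups alike, and nothing in the documents shows that it distorts the comparison between them. That prophylaxis was withheld because of bleeding risk is conjecture.

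**What to change.** Keep exclusion 4 as it is. Then:

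1. In SAP section 10 and Protocol 9.7, change the surgery window to *within 3 months before the date of VTE diagnosis (cohort entry)*.
2. Label the Table 1 row and the Table 19 stratum *among patients with no recorded anticoagulant (UFH, LMWH, warfarin, NOAC) in the 12 months before the VTE encounter*. Stating which claim date the encounter refers to would make the label exact.
3. Report the number of patients with a listed orthopaedic procedure code whom exclusion 4 removes. This replaces the assumed q with a count and lets readers judge the selection.

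The cost is wording in two documents, one extra count using procedure codes already listed, and a slightly narrower stated scope. No main result changes.

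A sensitivity analysis that re-admits patients whose only earlier anticoagulant was perioperative is not needed. For the hazard ratios it would break the new-user design and would need a new rule for the index date and index drug, and new propensity scores in four comparisons. If wanted, it should be optional and confined to the Table 1 frequency.
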